11.2. Sample Size

The NZ site and USA site will recruit 20 and 80 patients, respectively. These values are based on an estimated drop-out rate of 20% and the requirement for a minimum of 80 patients in total to assess feasibility and provide robust information in respect of appropriate outcome measures.

11.3. Pass/Fail Criteria

There will be no pass/fail criteria as this is a feasibility study for evaluation of outcomes for subsequent trial design.

11.4. Statistical Termination

There will not be a statistical interim analysis. Therefore no criteria for termination on statistical grounds.

11.5. Statistical Procedure Deviations

Any deviation(s) from the original statistical plan will be described and justified in the protocol or final report, as appropriate.

11.6. Selection Criteria

For endpoint details see section 9.4. All participants who were screened to take part in the study will be included in the analysis of endpoint 2.b.i. All patients who were discharged with a myAIRVO 2 device to take home will be included in analysis of all other endpoints.

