9.4. End Points

The following end points will be evaluated:

Primary outcome:

The primary outcome will be NHF use for 30 days following discharge after AECOPD. Use will be expressed as hours of myAIRVO 2 use per day over 30 days, as obtained by myAIRVO 2 electronic monitoring.

Secondary outcomes:

Other use variables:

- i. Number of days of use, adjusted for number of days with myAIRVO 2 at home
- ii. Average use per day of myAIRVO 2 during week 1, week 2, week 3 and week 4.
- iii. Average use per day on days of myAIRVO 2 use

Withdrawals and exclusions:

- i. Proportion of participants screened that were excluded
- ii. Reason for exclusion
- iii. Proportion of participants enrolled that were withdrawn
- iv. Reason for withdrawal

Participants requiring oxygen delivery via myAIRVO 2:

- i. Proportion of participants using domiciliary oxygen

Aspects of myAIRVO 2 use:

- i. Proportion of participants who reported having reduced myAIRVO 2 flow settings from the initial flow
- ii. Reduction in flow
- iii. Proportion of participants who reported having increased myAIRVO 2 flow settings from the initial flow
- iv. Increase in flow
- v. Proportion of participants who reported having reduced myAIRVO 2 temperature setting from the initial setting
- vi. NHF therapy Questionnaire results

Clinical outcomes

- i. Proportion of participants with at least one hospital readmission within 30 days of discharge
- ii. Reasons for hospital admissions (AECOPD, other respiratory cause or other cause)
- iii. In those that had at least one hospital readmission:
 - a. Number of readmissions
 - b. Time to first hospital readmission
 - c. Hospital readmission length
- iv. Proportion of participants with at least one ED visit within 30 days of discharge
- v. Reason for ED visits (AECOPD, other respiratory cause or other cause)
- vi. In those that had at least one ED visit:
- vii. Number of ED visits
- viii. Time to first ED visit
- ix. Proportion of participants with at least one GP visit within 30 days of discharge
- x. Reason for GP visits (AECOPD, other respiratory cause or other cause)
- xi. In those that had at least 1 GP visit within 30 days of discharge: number of GP visits
- xii. LACE Index for hospital admissions
- xiii. Lung function measurements (FEV₁, SVC_{in} and FVC) at day 1 and 31.

* An ED visit is counted if the patient went to ED for assessment and was not subsequently admitted to a hospital ward.

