9.9. Point of Enrolment

Participants will be considered enrolled and part of the study population at the time the inclusion and exclusion criteria have been met on the first visit in hospital. This will be after the Consent Form has been signed by both the Participant and Study Investigator.

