9.10.3. Pre-discharge assessments and training

- a.** Participants will be approached at least one day prior to expected discharge to ensure familiarity with NHF therapy prior to discharge. Written informed consent will be obtained (see participant information sheets and consent forms).
- b.** Demographic data collection will include: Date of birth, gender, year of COPD diagnosis, presence of alpha antitrypsin deficiency, other respiratory conditions, current medications, pack year history (a pack year is defined as twenty cigarettes smoked every day for one year, for a calculator see <http://smokingpackyears.com/>), LACE index score and if domiciliary oxygen is prescribed. The Investigator will update the Medical History Log and Medication Log. The last recorded spirometric values in the participant's clinical records will also be documented.
- c.** Participant inclusion and exclusion criteria (Section 9.8) will be assessed, and ineligible patients excluded.
- d.** Participants will be allocated a myAIRVO 2 device and the device serial number will be recorded.
- e.** A training session on how to use myAIRVO 2 will be performed by the study investigator (Appendix 2). The participants' next of kin will be encouraged to be present at this session. Familiarization and acclimatization to the device and the therapy will also be conducted prior to leaving the hospital. Where possible any issues regarding the device or therapy will be addressed prior to discharge. The participant will also be given the myAIRVO 2 user manual and 'Quick guide sheet' to read prior to the home visit and a phone number to contact the investigator with any questions during business hours.
- f.** For participants on oxygen only: If possible, oxygen saturation testing on the participant's usual home oxygen flow will take place during the hospital admission. The participant will be placed on their home oxygen prescription while sitting at rest for at least 5 minutes. Should the participant's oxygen saturation levels on their prescribed oxygen be $<88\%$ or $\geq 95\%$ they will be withdrawn from the study and referred for review of their home oxygen prescription.

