- g.** The investigator will confirm with the participant preferably on day of discharge, if they would still like to continue in the study. The Investigator will update the CRF, including the Medical Contact Log, Medical History Log, Medication Log and AE/SAE forms as required. The device plus consumables and any participant paperwork required for the study will be made available prior to discharge or taken to the patients home on the day of or day after being discharged from the hospital..

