9.11. Withdrawal Criteria

Participants are able to stop the intervention at any time, without being withdrawn from subsequent portions of the study. Participants may withdraw from the entire study at any time without giving a reason. Participants may be withdrawn at the discretion of the Investigator for any reason that is believed may present a safety risk.

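### Section 11.6 gives exclusion reasons and both withdrawal endpoints the wrong analysis set: no excluded patient is in it, and withdrawals before discharge drop out

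*Combined protocol and SAP*

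**What the plan says.** Section 11.6 defines two analysis sets. Everyone screened is used for an endpoint labelled 2.b.i. For the rest: "All patients who were discharged with a myAIRVO 2 device to take home will be included in analysis of all other endpoints".

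The withdrawals and exclusions group in 9.4 has four items: the proportion of those screened who were excluded; "Reason for exclusion"; "Proportion of participants enrolled that were withdrawn"; and the reason for withdrawal. The label 2.b.i is not visible in 9.4 in the copy reviewed, but only the first item is about people screened, so the other three fall to the device set.

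Section 9.9 fixes enrolment at the first hospital visit, after consent: "Participants will be considered enrolled and part of the study population at the time the inclusion and exclusion criteria have been met".

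Several provisions allow someone to leave after that point and before discharge:

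- 9.10.3 a: "Participants will be approached at least one day prior to expected discharge", so there is an interval between enrolment and discharge.
- 9.10.3 f: oxygen users whose in-hospital saturation test, done where possible, is out of range: "they will be withdrawn from the study and referred for review of their home oxygen prescription".
- 9.10.3 g: "The investigator will confirm with the participant preferably on day of discharge, if they would still like to continue in the study".
- 9.11: "Participants may withdraw from the entire study at any time without giving a reason".

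**The concern.** Section 11.6 is the plan's only statement of who is analysed for which endpoint, and for three endpoints it names a set that does not match the endpoint.

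For exclusion reasons, the mismatch is with the screened population: the people described are not in the assigned set at all. For the two withdrawal endpoints, the mismatch is with the enrolled population of 9.4 and 9.9: the assigned set starts later and has already lost the earliest leavers.

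Objective 2 in 8.2 asks what share of potential participants could go forward to the planned randomized trial, and these four items are the data for it. Section 7.2 also says the study will inform recruitment projections and design changes. Therapy starts in hospital for acclimatization (9.10.2 b), so a participant who finds it intolerable may leave before going home. That is information a feasibility study should report.

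**Working it through.** **The plan's own figure.** Section 11.2 gives a minimum of 80 patients and 20% drop-out. 80 / (1 − 0.20) = 100, which matches the 100 in 9.12. The illustration below therefore uses N = 100 enrolled and 20 withdrawals in total.

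**Exclusion reasons.** No arithmetic is needed. A patient excluded at screening is not discharged with a study device, so the 11.6 set holds no one with an exclusion reason, whatever happens in the trial.

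**Withdrawal proportion.** Let k be the number withdrawn before discharge and b the number withdrawn after.

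- Under 9.4 and 9.9: (k + b) / N
- Under 11.6: b / (N − k)
- Difference: k(N − k − b) / [N(N − k)]

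The difference is never negative. It is positive whenever k ≥ 1 and not everyone withdraws, so the direction does not depend on the value of k.

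With N = 100 and k + b = 20, the 9.4 value is always 20/100 = 20.0%, and the 11.6 value is (20 − k) / (100 − k). The documents do not give k; the values below are assumptions.

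| k | 11.6 value | 95% Wilson interval | Understatement (points) | Reasons unreported (k/20) |
|---|---|---|---|---|
| 0 | 20/100 = 20.0% | 13.3 to 28.9% | 0 | 0% |
| 1 | 19/99 = 19.2% | 12.6 to 28.0% | 0.8 | 5% |
| 2 | 18/98 = 18.4% | 11.9 to 27.2% | 1.6 | 10% |
| 3 | 17/97 = 17.5% | 11.2 to 26.3% | 2.5 | 15% |
| 5 | 15/95 = 15.8% | 9.8 to 24.4% | 4.2 | 25% |

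Check by the difference formula at k = 5: 5 × 80 / (100 × 95) = 400/9500 = 4.2 points.

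Every interval in the table contains 20%, so over this range the shift is small beside sampling error. If half of the withdrawals came before discharge (k = 10), the 11.6 value would be 10/90 = 11.1%, an understatement of 8.9 points. Nothing in the documents indicates that k would be that large.

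**The case against.** The best defence is that 11.6 itself sends the reader to 9.4 for endpoint details, and 9.4 puts the denominator in the name of each proportion. On that reading the specific definition prevails. Section 11.6 says device patients are included, not that only they are, and no analyst would tabulate exclusion reasons on a set without excluded patients. A sensible analyst may well do the right thing. The two sections would still disagree, and departing from the set named in 11.6 could be read as a deviation to be described and justified under 11.5. If 11.6 is not meant to be restrictive, it names no set for these endpoints and needs the same correction.

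It can also be said that the effect is conditional and small. This stands. k may be zero. The in-hospital saturation test covers oxygen users only, is done where possible, and is repeated under 9.10.5 b, so some of those withdrawals will fall after discharge. The endpoints are secondary and descriptive, 11.3 sets no pass/fail criteria, and withdrawals before discharge do not affect the primary outcome.

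A further point is that the calculation removes early leavers from both numerator and denominator. If the enrolled denominator were kept and only the numerator restricted, k = 5 would give 15/100 = 15.0%, which is further from 20%, not nearer.

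**Conclusion.** The point holds; it should be fixed, but it does not threaten the study. For exclusion reasons, 11.6 as written assigns an empty set. This rests only on reading 2.b.i as the proportion of those screened who were excluded, the one item that fits. For the withdrawal endpoints, 11.6 followed as written understates the proportion and omits the earliest reasons as soon as one participant leaves between enrolment and discharge, unless everyone enrolled withdraws. On the plan's 20% drop-out, with 1 to 5 of 20 withdrawals assumed before discharge, the understatement is 0.8 to 4.2 points and 5% to 25% of reasons go unreported; with none before discharge there is no shift. The underlying data are collected and recoverable.

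**What to change.** Reword 11.6 so that each item in this group has its own set:

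- Proportion excluded: all screened, as now.
- Reason for exclusion: all excluded patients, from the eligibility screening log (9.10.6).
- Proportion withdrawn and reason for withdrawal: all enrolled as defined in 9.9, preferably split into before and after discharge. The documents do not say when the randomized trial would enrol, so both parts may be needed for planning.
- Remaining endpoints: keep the device set, worded so that it also covers participants whose device is brought to the home on the day of discharge or the day after (9.10.3 g).

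The domiciliary oxygen endpoint can stay as it is: 9.4 does not define it on those screened or enrolled, so 11.6 does not contradict it.

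The cost is one paragraph. No new data are needed, because exclusions are on the screening log and 9.10.7 lists an enrolment and withdrawal log. The only downside is a slightly less favourable withdrawal figure if anyone leaves before discharge.

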11.7. Statistical Data Management

As above. Data analysis will be with SAS 9.3

12. ADVERSE EVENTS AND TERMINATION

Fisher and Paykel Healthcare Data Safety Monitoring Board will review all SAE's.

12.2. Foreseeable Adverse Events

Participants may wish to discontinue NHF therapy should they find it uncomfortable. Adverse events are expected, including death, hospital and Intensive Care Unit admissions and patient deterioration as part of disease progression.

12.3. Reporting Adverse Events

For the purposes of this study the following events will be considered to be serious adverse events (SAEs):

- Death
- Life-threatening event

- Permanently disabling or incapacitating event
- Hospitalisation or prolongation of hospitalisation. Hospitalisation for the purposes of SAE reporting is defined as an admission to hospital and does not include a presentation to the ED followed by discharge without admission or an admission for elective reasons
- Any event considered serious by the study investigator

SAEs will be reported to the Sponsor (Fisher and Paykel Healthcare) within 24 hours of the investigator becoming aware of the event on the study SAE form. Other adverse events will also be reported to the Sponsor within seven days.

Other adverse events (AEs) will be reported to the Sponsor (Fisher and Paykel Healthcare) within 7 days of the investigator becoming aware of the event on the study AE form.

Device deficiencies (related to the identity, quality, durability, reliability, safety or performance of a device) will be reported to the Sponsor (Fisher and Paykel Healthcare) in writing. If the investigator deems the event could have led to a serious adverse event, it must be reported within 24 hours of the investigator becoming aware of it, otherwise it should be reported within 7 days. The sponsor will manage device deficiency reports as part of its ongoing post marketing safety review process and the investigator will supply the sponsor with additional safety information as required.

Adverse events and device deficiencies will be reported to the HDEC, IRB, Medsafe and FDA as required

12.4. Early Termination

Early termination may occur at the discretion of the Investigators for any reason that is believed may present a safety risk.

The following documentation is required if the appropriate party terminates a clinical trial.

12.4.1. Investigator

If the investigator terminates or suspends a trial without prior agreement of the Sponsor, the investigator should inform the institution, where required by the applicable regulatory requirements and the investigator/institution should promptly inform the sponsor and the IRB/IEC, and should provide the sponsor and the IRB/IEC a detailed written explanation for the termination or suspension.

12.4.2. Sponsor

If the Sponsor terminates or suspends a trial, the Sponsor should promptly inform the investigator. The investigator should then promptly inform the IRB/IEC and provide the IRB/IEC a detailed written explanation for the termination or suspension.

12.4.3. Institutional Review Board (IRB) or Independent Ethics Committee (IEC)

If the IRB/IEC terminates or suspends its approval/favorable opinion of a trial the investigator should inform the institution, where required by the applicable regulatory requirements, and the investigator/institution should promptly notify the sponsor and provide the sponsor with a detailed written explanation for the termination or suspension.

13. PUBLICATION POLICY

The study sites, represented by the principal investigator (PI), will take responsibility to report the results in an appropriate scientific venue. Publication of the study outcomes will comprise the study as a whole and is encouraged by the sponsor regardless of outcome. The sponsor retains editorial rights to protect the sponsor's proprietary information and intellectual property.

16. APPENDIX 1: FLOWCHART

17. APPENDIX 2: TRAINING SESSION REQUIREMENTS

Hospital Acclimatization/Familiarization session

Instruction	myAIRVO 2 manual reference
Familiarize and acclimatize participant to NHF therapy using myAIRVO 2, this should include a period of NHF use by the participant.	N/A
Explain warnings on page A-2 of myAIRVO 2	A-2
Explain how myAIRVO 2 works and what each of the consumables are for	A-3
Demonstrate switch on and startup of myAIRVO 2 and document participant's nasal cannula size (small, medium or large)	A-7
Instruct participant to change temperature setting and NOT activate junior mode	A-8 to A-9
Participants NOT on domiciliary oxygen: Demonstrate how to change target flow OR Participants on domiciliary oxygen only: Demonstrate how to connect oxygen tubing, explaining warnings for oxygen use & instruct participant NOT to change myAIRVO 2 flow setting	A-8 A-10
Demonstrate how to put myAIRVO on night mode	A-9
Give participant myAIRVO 2 manual and 'Quick guide' sheet	N/A

Full training Session at home visit:

Instruction	myAIRVO 2 manual reference
Explain warnings on page A-2 of myAIRVO 2	A-2
Re-explain how myAIRVO 2 works and what each of the consumables are for	A-3
Demonstrate startup of myAIRVO 2 including: 
 - Position of AIRVO - Water chamber instillation, and that distilled water must be used - How to check water level and to avoid letting water run out - Installation of heated breathing tube 	A-4 to A-6
Demonstrate how to switch on myAIRVO 2 including: 
 - Switch on - Warm up screen - Connection of patient interface 	A-7
Explain the drying mode and that should the participant wish to use myAIRVO 2 while it is in drying mode they can override it by pressing the main button twice or switching it off then on at the wall.	A-7
Participants NOT on domiciliary oxygen: Demonstrate how to change target flow OR Participants on domiciliary oxygen only: Demonstrate how to connect oxygen tubing, explaining warnings for oxygen use & instruct participant NOT to change MyAIRVO 2 flow setting	A-8 A-10
Instruct participant NOT to activate junior mode	A-8 to A-9
Demonstrate how to put myAIRVO 2 on night mode	A-9
Show participant where the alarms section is in the manual is and advise to: 
 - Consider contact with investigator if the 	A-11 to A-12


alarm sounds.
 
 - Contact with investigator MUST take place if the "Fault (E####) message is displayed 	
Explain daily and weekly cleaning and maintenance regimens	A-13
Explain that there is a spare set of cannulas available should the participant soil theirs, and to contact the Investigator if more cannulas are needed	A-14
Instruct that the Filter in new and must NOT be removed, tampered with or replaced.	A-14

Ensure participant still has the 'Quick guide' sheet at front of myAIRVO 2 manual and reiterate that:
 
 - Participants can call during business hours with questions - myAIRVO 2 does NOT provide life support and should NOT be used to treat worsening symptoms, participant's should instead seek medical help - If unsure, do not use myAIRVO 2 until contact has been made with one of the Investigators - myAIRVO 2 should NOT be left running when not in use. The only exception to this is if the participant removes it for a very short period of time (e.g. to go to the bathroom or make a drink) 	N/A

